10.1.1 ENDPOINTS AND RATIONALE

To ensure patient-centered endpoints, we twice met with patients and caregivers through two community engagement studios.⁵⁴ Patients prefer to be healthy and have a good QoL. If a safe alternative is available, patients prefer not to be hospitalized.

The **primary outcome** is **days alive and out of hospital (DAOOH) at 30 days post-randomization**. Unlike time-to-event analyses that ignores repeat events and gives equal weight to components of a composite endpoint,⁵⁵ DAOOH accounts for both frequency and duration of hospitalization and also weights mortality most heavily.^{55,56} This endpoint has also been suggested as a quality metric rather than re-hospitalization alone.⁵⁷

The **two secondary outcomes** are 1) **QoL using the KCCQ**. Patients desire not only to live longer, but to live better; or at minimum, not be worse after an acute health care related event.⁵⁸ Patients with advanced HF would trade survival time (or days alive) for a better QoL.⁵⁸ Our pilot work supports the feasibility of assessing QoL in the acute setting and suggests changes in scores are related to hospital re-visits.⁵⁹ We hypothesize that fewer days in the hospital in our SSU arm will also lead to a greater QoL. Interviews of hospitalized AHF patients suggest **they would prefer a shorter hospital stay or avoid an admission altogether**, assuming safety and outcomes are similar or better than hospitalization. Thus, assessing QoL is a key aim.

The KCCQ is a patient-reported, validated survey instrument designed to measure QoL in chronic HF patients.⁶⁰ Lower scores equal lower patient-reported QoL. **KCCQ scores predict adverse outcomes – namely hospitalization and mortality.** Importantly, the KCCQ demonstrates responsiveness to clinical change.⁶⁰⁻⁶²

A change of five points has been previously shown to be clinically significant, and will be assessed prior to discharge and day 30 post-randomization.⁶²

2) Cost effectiveness analysis, described in detail below.

NOTE: For patients randomized to SSU who worsen PRIOR to going to SSU, this will be counted the same as a hospitalization from the SSU.

ADDITIONAL ENDPOINTS

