10.4.3 ANALYSIS OF THE SECONDARY ENDPOINT(S)

QoL: An AHF SSU strategy of care will lead to significant improvement in QoL scores at 30 days post-discharge compared with usual care. QoL will be assessed with the KCCQ.⁵⁹

Sample Size Calculation: The standard deviation of 1-week KCCQ change after acute heart failure is 20.8.⁷³ Below are the numbers of subjects (both arms combined) required to detect various intervention effects with 80% power and type I error controlled at 0.05 (two-sided) in the table.

Similarly, the number of subjects (both arms combined) required to detect various effect size for caregiver burden (CB) with 80% power and type I error controlled at 0.05 (two-sided) is listed below. The effect size is defined as the difference in CB score divided by the standard deviation. It is a widely-used measure of treatment effect, which is used here because the standard deviation of CB in the target population if it has not been robustly studied. Because we changed CB scales, we will use established MCID for each established scale.

KCCQ: Sample size (both arms combined)	% of data attrition	Difference in KCCQ change
480	10%	5.3
360	33%	6.2
240	55%	7.6
120	78%	10.7

KCCQ QoL Analysis: The KCCQ will be compared between the two arms using the same method as in Aim 1. We will consider three ways of analysis with different outcomes based on KCCQ scores. First, we will exclude subjects who die without KCCQ in the analysis. Second, we will set KCCQ=0 for those who die without the 30-day KCCQ and include these people in the analysis. Third, we will create a composite binary endpoint of KCCQ<c or death, where c is a threshold. Chi-square test and logistic regression will be used to compare this outcome. We will select several relevant values for the threshold c and tabulate the results. The three analysis schemes allow us to understand how robust the comparison of KCCQ is with respect to different treatments of death.

Cost-Effectiveness Analysis:

To assess the effectiveness of short stay unit (SSU) management, we will analyze the patient outcomes as defined by cost, quality-of-life (QOL), medical utilization, and caregiver burden using regression analysis, and combine these results into a multifaceted incremental cost-effectiveness ratio (ICER).

$$ICER = \frac{C_{SSU} - C_H}{E_{SSU} - E_H}$$

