Given the difficulty of obtaining costs and payments, we will standardize hospitalization and SSU costs using Medicare reimbursement rates (See Sensitivity Analysis Section below). Patient costs will include self-reported out-of-pocket costs and time costs using a modified version of a previously published survey. (see attached) One limitation of self-reported data will be potential mismeasurement due to recall bias. Should the patient-completed survey lack a sufficient response rate for outpatient analysis, we will limit our analysis to the hospital portion of the treatment. Effectiveness will be defined by SF-12 and SF-6D metrics of patient self-reported QOL. The SF-12 has been previously used to evaluate outcomes for HF patients.³ Effectiveness in ICER computations is often measured using quality-adjusted life years (QALYs), defined as:

$$QALY = \sum_{t=t_0}^Z \delta^{t-t_0} q_t P_t$$

where P_t is the probability of surviving to each year t , q_t is the preference weight, and δ is the time-discounting factor. As the SF-12 does not allow direct assessment of QALYs, we will convert the score into a SF-6D preference based score using the six health dimension scores from the SF-12^{4,5} to generate the preference weights and probabilities necessary to conduct the cost-utility analysis. Since the participant will be completing the SF-12 survey at the beginning and end of the episode, all models estimating the effectiveness will include the baseline score in the vector of participant characteristics. Aside from cost and effectiveness, we will analyze the incidence of re-admission, the utilization of outpatient care, and caregiver burden, as detailed in our statistical analysis plan. While the incidence of re-admission will be obtained from both the electronic health record and patient self-report, the outpatient and caregiver burden are self-reported.

For each outcome variable of interest (patient costs, hospital costs, total episode costs, SF-12 scores, SF-6D scores, QALYs, incidence of readmission, total days of hospitalization, utilization of outpatient care, nursing care, and caregiver burden) we will estimate a predictive model accounting for the heterogeneity among participants in the intervention and control groups.

$$Y_i = \alpha + \beta_1 SSU_i + \beta_2 D_i + \beta_3 R_i + \beta_4 D_i * R_i + \beta_5 D_i * SSU_i + \beta_6 R_i * SSU_i + \beta_7 D_i * R_i * SSU_i + \gamma X_i + \delta H_h + \kappa_h + \tau_t + \varepsilon_i$$

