where, Y_i is the outcome of interest for participant i described in the following paragraph. SSU_i is an indicator if the participant was assigned to the SSU treatment, D_i are the total number of hospital inpatient days, R_i is an indicator for a readmission. The interaction terms $D_i * R_i$ and $D_i * R_i * SSU_i$ differentiate between continuous inpatient days and inpatient days separated with a readmission, for hospital admission and SSU group respectively. The interaction terms $D_i * SSU_i$, and $R_i * SSU_i$ capture the effect of SSU on inpatient days and readmission rates. X_i is a vector of participant characteristics (age, gender, insurance status, etc.), H_h is a vector of hospital characteristics, κ_h , τ_t are hospital, and year fixed effects, and ε_i is an independent and identically distributed error term. The effect of the SSU assignment on the outcome measure will be captured by coefficients β_1 , β_5 , β_6 , β_7 , unbiased and consistent estimators of the intervention effect because of the random assignment of participants.

When estimating the re-admission rate, we will use a probabilistic model such as:

$$\Pr(R_i) = F(\alpha + \beta_1 SSU_i + \beta_2 D_i + \beta_3 D_i * SSU_i + \gamma X_i + \delta H_h + \kappa_h + \tau_t + \varepsilon_i)$$

where the probability of readmission will be a function of intervention status, SSU_i , days of inpatient care, D_i , the interaction between these, $D_i * SSU_i$, participant characteristics, X_i , vector of hospital characteristics, H_h , and fixed effects, κ_h , τ_t , and ε_i is an independent and identically distributed error term. The choice of the functional form for this model will depend on the incidence of readmission in the data

Random assignment to SSU will be tested in pre-analysis by comparing the means of the intervention and control group characteristics using t-tests, and probability of being assigned to intervention group conditional of participant characteristics, particularly health status.

Sensitivity Analysis for CEA

To test the robustness of our estimates, in view of the assumptions made about cost, the choice of effectiveness measure, and the probability specification function for readmission, we will re-evaluate our results with alternative definitions.

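### The cost-effectiveness models adjust for inpatient days and readmission, which follow randomization, so their SSU coefficients are not unbiased intervention effects

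*Combined protocol and SAP*

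**What the plan says.** The Cost-Effectiveness Analysis in section 10.4.3 uses one regression equation for every outcome: patient, hospital and episode costs, SF-12, SF-6D, QALYs, and also "incidence of readmission, total days of hospitalization, utilization of outpatient care, nursing care, and caregiver burden". The right-hand side holds the SSU indicator, D, R, D×R, and the interactions of all three with SSU, plus participant and hospital characteristics and fixed effects. D is "the total number of hospital inpatient days" and R marks a readmission.

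The SSU effect is read from the coefficients on SSU, D×SSU, R×SSU and D×R×SSU (beta1, beta5, beta6, beta7). These are called "unbiased and consistent estimators of the intervention effect because of the random assignment of participants". The D×SSU and R×SSU terms are also said to "capture the effect of SSU on inpatient days and readmission rates".

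A separate readmission model follows, "where the probability of readmission will be a function of intervention status", with D and D×SSU kept as covariates. The section says it will "combine these results into a multifaceted incremental cost-effectiveness ratio" but does not say how. On covariates it adds that "all models estimating the effectiveness will include the baseline score in the vector of participant characteristics".

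**The concern.** D and R are both measured after assignment. Randomization protects a comparison of arms given baseline; it does not protect a comparison among patients with the same inpatient days and the same readmission status. Fewer inpatient days is also the main route by which the SSU is expected to save money. Section 10.1.1 names the same route for quality of life: "We hypothesize that fewer days in the hospital in our SSU arm will also lead to a greater QoL". Holding D fixed removes that route from the coefficient. It can also add selection bias, because the sicker SSU patients are the ones likely to be admitted.

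Cost-effectiveness at 30 days is one of two secondary endpoints. If the coefficients enter the ICER, the saving through days leaves the numerator and any quality-of-life gain through days leaves the denominator. The readmission model could report harm that is not there.

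**Working it through.** **Two points that need no assumed figures.**

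1. Total days of hospitalization is both an outcome and, as D, a covariate. Regressing D on itself gives a coefficient of 1 on D and zero on every SSU term. This was confirmed by fitting: a true difference of -1.0 day returned SSU coefficients of 0.
2. D×SSU measures whether the slope of the outcome on D differs by arm. It does not measure the SSU effect on D. In the cost simulations below, mean beta5 lay between -3 and +3 dollars per day although the SSU cut D by 3.0 days.

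**Inputs from the documents.** Section 10.5: mean stay 5 days, 40% of SSU patients admitted, DAOOH SD 3.9, 240 evaluable per arm, design difference one day. Section 2.2: a 30-day readmission rate of 12.5%. The plan gives no cost or ICER figure to reproduce. Its sample size does reproduce: 2 × (1.96 + 0.84)² × 3.9² / 1² gives 239 per arm, about 240 with a small O'Brien-Fleming inflation, and 240 / 0.9 gives 267 per arm, 534 in total.

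**Algebra.** Let an inpatient day cost c, let the SSU save d days, and let the SSU have other costs s. With cost = a + c·D + s·SSU + error:

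- total effect of assignment = s - c·d
- SSU coefficient with D in the model = s, plus any selection bias

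If SSU time is not inpatient time, d = 5 - 0.4 × 5 = 3.0. If one SSU day is counted in D, d = 5 - (1 + 0.4 × 5) = 2.0.

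**Cost simulation** (240 per arm, 400 runs per cell). Index stay is gamma with mean 5 and SD 3.9 (SD assumed equal to that of DAOOH). Readmission is 12.5% in both arms and adds a stay with the same distribution. Residual SD is $1,500. The values of c and s are assumed. Each cell gives the arm difference, then beta1, in dollars:

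| c per day | s = -1,000 | s = 0 | s = +700 | s = +2,000 |
|---|---|---|---|---|
| 1,000 | -3,987; -1,001 | -3,016; -15 | -2,286; +692 | -964; +2,014 |
| 2,000 | -6,965; -990 | -5,974; +2 | -5,328; +692 | -3,995; +1,998 |
| 3,000 | -10,042; -998 | -8,966; -12 | -8,318; +688 | -7,014; +2,004 |

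Beta1 returns s throughout. The share of the saving lost is c·d / (c·d - s). At s = -1,000 it runs from 3,000 / 4,000 = 75% to 9,000 / 10,000 = 90%; at s = 0 it is essentially all. The sign reverses only when 0 < s < c·d. Unmeasured severity worth $500 to $1,000 per SD moves beta1 up by about $80 to $205. With d = 2.0, c = $2,000 and s = 0, the figures are -$4,001 and +$4.

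**Smaller effect on days.** In a separate simulation the SSU shortens the index stay by one day, with $1,000 per day and an assumed $3,000 per readmission. The arm difference is -$859, beta1 is -$26, and the four SSU terms averaged over a common D and R give -$21. If unmeasured severity (assumed $2,000 per SD) drives days, readmission and cost, that averaged contrast becomes +$334 against a true -$852.

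**Quality of life.** With an assumed total effect of +3 points (SD 10), the SSU coefficient is 2.98, 1.51 or 0.06 when 0%, 50% or 100% of the effect runs through days. In the last case, with c = $2,000 and s = 0, arm differences place 100% of simulated trials in the quadrant where the SSU is cheaper and better. The coefficients place 26% there and 24% in the opposite quadrant.

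**Readmission model** (no true SSU effect, 12.5% in both arms, 1,000 runs per cell). The grid takes SSU admission at 20% or 40%, mean readmission stay of 3 or 5 days, and 0 or 1 SSU day counted in D. The arm-only odds ratio is 1.00. At mean D, the modelled SSU odds ratio is 1.36 to 2.76, with false-positive rates of 16% to 80%. For beta1 alone it is 1.14 to 1.81, with rates of 3.5% to 19%. The cause is that D includes readmission days: at a given total, SSU patients have fewer index days, so more of the total tends to come from readmission.

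**The case against.** The strongest reply is that the ICER is defined from arm-level cost and effectiveness, and the regression is called predictive. If each arm's fitted values are averaged over that arm's own D and R, the arm difference is recovered exactly (-$859 in the one-day example). That is correct, and on that reading the ICER is unharmed. But the plan does not state the step; it reads the effect from the coefficients. The harm to the ICER is therefore conditional, while the claim about the coefficients is wrong either way.

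Second, the dollar figures depend on assumed costs and on a derived 3.0 days, whereas the stated design difference is one day. This also stands. The one-day simulation loses the saving too, so the mechanism does not depend on 3.0.

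Third, readmission is partly guarded. Its model is offered only as an example, and the Sensitivity Analysis for CEA describes readmission odds by SSU status. The composite of death and re-hospitalization in section 10.4.3.1 is compared by arm without D. The false-positive rates for beta1 are much milder than those at mean D. If D counted index-stay days only, the odds ratios would be 0.92 to 0.99 with 2% to 6% false positives. However, D is defined as total days, and the sensitivity text does not say whether D stays.

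Finally, the total-days identity would be noticed at once when fitted. It is a drafting error, but it should still be corrected.

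**Conclusion.** The concern holds. Random assignment does not make the SSU coefficients unbiased for the intervention effect when inpatient days and readmission are in the model. The plan also misreads the D×SSU and R×SSU terms and uses total days as both outcome and covariate. None of this depends on assumed costs.

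The effect on the ICER is conditional on the coefficients feeding it. In that case the saving through days is lost: 75% to 90% of the total saving if the SSU also saves $1,000 elsewhere, and practically all of it if the SSU has no other cost effect. These sizes rest on $1,000 to $3,000 per day, 3.0 days saved and no severity confounding. A change of sign is possible but not certain. No listed sensitivity analysis drops D and R from the cost or effectiveness models.

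This should be fixed because it affects a secondary endpoint. The primary DAOOH comparison, the sample size and the arm comparisons of death and re-hospitalization are unaffected.

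**What to change.** - Estimate incremental cost and incremental effect for the ICER from models with assigned arm, site, year and pre-randomization covariates only.
- State how the regression results enter the ICER, and report incremental cost and incremental effect separately, with intervals, beside it.
- Remove D and D×SSU from the readmission model, and state in the Sensitivity Analysis for CEA that D is not a covariate there.
- Do not fit the D and R model to total days or, in its linear form, to readmission.
- Keep any model with D and R only as a labelled descriptive or mediation analysis. Delete the claim of unbiasedness and the statement that the interactions give the SSU effect on days and readmission.
- Reconcile the SF-12 timing. Section 10.4.3 relies on a baseline score, but the Schedule of Events Table (7.3.7) first lists SF-12 at pre-discharge in each arm, after assignment. Adjust for the score only where it was taken before randomization; otherwise leave it out.

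The cost is SAP wording and a little analysis work. No new data are needed.

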10.4.3.1 ADDITIONAL ANALYSES

Exploratory Analyses: As observation is not an admission, payers cover out of pocket costs differently.

Guideline Adherence: Adherence to HF guidelines at time of discharge in the SSU arm is equivalent or better than adherence in the usual care arm.

Sample Size Calculation: We assume that the adherence percentage is 85% in the control arm.⁶⁴ With 240 subjects in each arm, we will have 80% power to detect an absolute improvement of 8% in the SSU arm, where the type I error rate is controlled at 0.05 (two-sided). Adherence to HF-Guidelines will be assessed based on the established Get-With-The-Guidelines HF (GWTG-HF) metrics for eligible patients. These measures have been previously well established.^{64,74}

HF Guideline Adherence Analysis: Fisher's exact test will be used to compare the percentage of adherence. Please see below regarding sensitivity analysis and missing data approaches.

CB Scale: Sample size (both arms combined)	% of data attrition	Effect size in CB scale
480	10%	0.25
360	33%	0.30
240	55%	0.37
120	78%	0.51

Caregiver Burden Analysis: This will be similar to the KCCQ analysis. See table for sample size considerations.

Sub-group analysis: The nature of the sub-group analysis is exploratory and will be used to generate hypotheses for future testing. We will study four pre-specified sub-groups: 1) older patients, defined as greater than 75 years old; 2) gender; 3) race and 4) insurance status (Medicaid, self-pay, Medicare, Commercial). The rationale for selecting these sub-groups is based either on known cardiovascular disparities or there is limited data regarding an SSU strategy in these specific subgroups.⁴⁶ The hypothesis: there will be no differences in outcomes, QoL, or guideline adherence between any of these groups. If the primary endpoint is achieved, we aim to demonstrate the AHF SSU strategy is broadly applicable across all subgroups. If there are differences, however, this may either demonstrate areas in need of further study, or initial subgroups to target. To test these hypotheses, we will compare the treatment benefit between sub-groups by formal two-sample testing procedures using normal approximation (e.g. Z test). A permutation test will also be performed as a sensitivity analysis. Given the limited sample size and the exploratory nature of the sub-group analysis, no multiple comparison adjustment will be made for these tests.

Intervention Monitoring: To ensure fidelity of each component of the intervention between study arms, we will also measure the following individual components of the intervention throughout the trial at both the site and overall study level: 1) Baseline patient characteristics, 2) Medicine reconciliation 3) Guideline-HF adherence 4) SSU AHF protocol adherence, 5) admission rates from the SSU 6) Quality of Life/Caregiver Burden Questionnaire response and completeness, 7) Hospitalized patients discharged within 48 hours, and 8) Follow up completed at 30 days. These analyses will be reported every 3 months to the Steering Committee to allow for course correction as needed. In addition, these will be reported at the conclusion of the study as well as at quarterly enrollment milestones to the DSMB.

Sensitivity Analyses: Some baseline covariates such as co-morbidities, medications, renal function, serum sodium, potassium, b-type natriuretic peptide (BNP) or NT-pro BNP, and blood pressure, may not be well-balanced between the two arms despite randomization. These covariates are known markers of risk in AHF patients and are part of the standard assessment for the vast majority of AHF admissions. We will use the inverse probability weighting approach to adjust those covariates with poor balance between the arms as part of a sensitivity analysis.⁷⁵ We will then compare these results with those from the two-sample t test. In addition, if the DAOOH, QoL, caregiver burden, or mRUQ-HF endpoints are found to be non-normal in distribution, the Wilcoxon Rank-Sum test will be used for comparison as a sensitivity analysis.

Modified Resource Utilization Questionnaire for Heart Failure (mRUQ-HF).⁷⁰ The mRUQ-HF is a 14-item self-report questionnaire of comprehensive lists of choice related to healthcare utilization. (See Appendix trial protocol) Exploratory analysis will occur in two steps: 1) Determination of resources consumed or related; 2) Assignment of 'value' to the resources consumed.⁷¹ This two-step process allows for transparency of assigned costs. Hospital costs will be assigned per individual hospital cost-accounting. Where monetary values are not directly self-reported, Medicare fee schedules will be used for uniformity. This will be captured at 90 days and will include the hospitalization when patients answer the questionnaire.

All Cause Mortality and All-Cause Rehospitalization Endpoints:

A composite endpoint of all-cause mortality and re-hospitalization is defined as the time from the randomization to either all-cause death, or re-hospitalization. The two intervention arms will be compared using a log-rank test. Given the multiple hospitals, a stratified log rank test will be utilized.

To compare the proportions of patients who had either all cause mortality or re-hospitalization within 30 days and separately 90 days from randomization, a composite endpoint of all-cause mortality and re-hospitalization is defined as either 1 for patients who died or re-hospitalized with 90 days since randomization, or 0 otherwise. The two intervention arms will be compared using the Fisher's exact test or Chi-square test as appropriate.

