10.5 SAMPLE SIZE

A one-day difference in the length of hospital stay is a 20% reduction in the mean length of stay(LOS) of five days during hospitalization (median LOS =4.3 days).⁵⁰ Pilot data support the clinical significance of a one-day reduction,⁴⁵ and discussions with patients and caregivers confirms this finding. *While we anticipate achieving greater than a one-day difference, we have powered our study conservatively.*

$$N (\text{total}) = 534; \quad N_1 = 267; \quad N_2 = 267$$

Based on published data,⁴⁶ we project that DAOOH has a mean of 25.6 with a standard deviation of 3.9 in the control arm. A reduction of the mean DAOOH by one-day is the minimal clinically meaningful difference as determined through our patient engagement outreach.⁵⁴ An interim analysis when half of the outcome data are available will be performed. (See DSMB, section E6). Accounting for this with the O'Brien-Fleming spending function, 240 subjects per arm are required to achieve 80% power in detecting the one-day difference in DAOOH, where the two-sided type I error rate is controlled at 0.05. Assuming 10% attrition due to drop-outs and lost to follow up, this study requires a total of 534 subjects. This power calculation also takes into account a conservative estimate of 40% of patients being admitted to the hospital from the SSU arm. *DAOOH automatically accounts for death.* The maximal number of days alive and out of the hospital through 30 days post randomization is 30 days. If a patient were to die on day 8 post-randomization, her DAOOH would be 8. This would be compared to a patient who stayed in the hospital 3 days after randomization, but never returned to the ED or hospital or died through 30 days. DAOOH of this patient would be 27. If the same patient returned to the hospital on day 12 for 2 days, and again on day 24 for 2 days, their total DAOOH would be 23.

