10.6 MEASURES TO MINIMIZE BIAS

10.6.1 ENROLLMENT/ RANDOMIZATION/ MASKING PROCEDURES

Patients will be randomized 1:1 to one of the two study arms, but stratified by site to ensure equal site representation. A central computer generated randomization scheme with random block sizes of two, four, and six will be created, stratified by site. The REDCap randomization module will be utilized to generate the randomization schema and patient allocation.

Due the nature of the intervention and the clinical setting, this is an unblinded trial.

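### Minor: the 80% power stated for guideline adherence (85% vs 93%, 240 per arm) is not that of the Fisher's exact test named for the analysis, which has about 77%

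*Combined protocol and SAP*

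**What the plan says.** The power statement and the test both stand in section 10.4.3.1 (Additional Analyses), under Guideline Adherence.

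- Control rate: "We assume that the adherence percentage is 85% in the control arm".
- Power: "With 240 subjects in each arm, we will have 80% power to detect an absolute improvement of 8% in the SSU arm". The type I error rate is given as 0.05, two-sided.
- Test: "Fisher's exact test will be used to compare the percentage of adherence".

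The section does not say which test or formula produced the 80%, and no other section gives a power figure for adherence.

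The 240 per arm comes from section 10.5, which sizes the trial on days alive and out of hospital: "Assuming 10% attrition due to drop-outs and lost to follow up, this study requires a total of 534 subjects". That is 267 randomized per arm, and 267 × 0.90 ≈ 240 remaining. Section 10.6.1 fixes allocation at 1:1.

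The synopsis and section 4.2.3 list adherence as exploratory. It is also the whole of Aim 2 (section 3) and of Hypothesis 2 (section 10.2).

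**The concern.** A power figure should describe the test that will be run. Fisher's exact test conditions on both margins. With binary data its rejection region usually uses less than the nominal 5%, so at the same sample size it has less power than an uncorrected chi-square test. A figure taken from an ordinary two-proportion formula therefore overstates what Fisher's test delivers.

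What is at stake is limited to Aim 2. A reader of a non-significant adherence result would take the chance of missing a true 8-point improvement to be 20%. With the test as named and the numbers as stated, it is about 23%.

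**Working it through.** **Inputs.** Control 0.85; SSU 0.85 + 0.08 = 0.93; n = 240 per arm; two-sided alpha 0.05; power 80%; Fisher's exact test (all section 10.4.3.1). Allocation 1:1 (section 10.6.1). Adherence is treated as one yes/no outcome per patient, as Fisher's test requires.

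**Step 1: reproduce the 80%.** Use the normal approximation with pooled variance under the null and no continuity correction.

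- Mean rate (0.85 + 0.93)/2 = 0.89.
- Null standard error: √(2 × 0.89 × 0.11 / 240) = √(0.1958/240) = 0.02856.
- Alternative standard error: √((0.85 × 0.15 + 0.93 × 0.07)/240) = √(0.1926/240) = 0.02833.
- Power = Φ[(0.08 − 1.96 × 0.02856)/0.02833] = Φ(0.848) = 80.2%.
- Sample size for 80%: (1.96 × √0.1958 + 0.8416 × √0.1926)² / 0.08² = 1.529/0.0064 = 238.9, so 239 per arm.

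The plan's figure is reproduced. Two other uncorrected approximations also come close: unpooled variance gives 80.6% and the arcsine transformation 81.2%. With a continuity correction, power falls to Φ[(0.08 − 1/240 − 1.96 × 0.02856)/0.02833] = Φ(0.70) = 75.8%.

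**Step 2: power of the named test.** For each of the 241 × 241 possible tables, compute the two-sided Fisher p-value (summing tables no more probable than the one observed). Then add the binomial probabilities of the tables with p ≤ 0.05. The same enumeration was done for the uncorrected Pearson chi-square test.

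| 240 per arm | Power, 85% vs 93% | Actual size, 85% in both arms |
|---|---|---|
| Fisher's exact, two-sided | 76.8% | 3.7% |
| Pearson chi-square, uncorrected | 81.0% | 5.0% |

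The shortfall against the stated figure is 80 − 76.8 = 3.2 points. The unused alpha explains it: Fisher's actual size is 3.7%, 3.5% and 3.4% when both arms are at 85%, 89% and 93%.

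**Step 3: what would make the sentence true for Fisher's test.**

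- Larger sample, 85% vs 93%: 79.8% power at 256 per arm, 80.0% at 257.
- Larger difference, 240 per arm: 80.0% power at 85% vs 93.25%, a difference of 8.25 points.

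**Step 4: are the cells sparse?** At the pooled rate of 89%, the expected number of non-adherent patients is 240 × 0.11 ≈ 26 per arm; at 85% it is 36. Small expected counts do not force the use of an exact test here.

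**The case against.** The case for leaving the sentence alone has four parts.

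1. **The gap is within rounding.** The effect is given as a whole number, and 8.25 points still rounds to 8%. This is true and keeps the point minor, but a reader who enters 85%, 93% and 240 does not get 80% for the named test.

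2. **The assumed control rate matters as much.** Keeping the 8-point difference, Fisher's power at 240 per arm is 73.4% for 84% vs 92%, 76.8% for 85% vs 93% and 80.6% for 86% vs 94%. A one-point shift is worth as much as the choice of test. This stands as a comment on materiality. It does not correct the figure for the rates the plan chose.

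3. **The analysed number may not be 240.** Adherence under Aim 2 is assessed at discharge, before most attrition. If all 267 per arm were evaluable, Fisher's power would be 81.7% and no shortfall would remain. But section 10.4.3.1 limits assessment to eligible patients, which works the other way: at an assumed 216 or 200 per arm, Fisher's power is 72.3% or 68.2%. The documents do not settle the evaluable number, so a reader should not infer that the realised power will be 77%. That figure belongs to the sentence as written.

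4. **Fisher's test is valid.** It holds the type I error at or below 5%, and preferring Pearson's test is a matter of judgment. This is accepted. The error lies in the pairing of test and power figure, not in the choice of test.

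A reader might also infer that the sponsor is shown to have used the uncorrected chi-square formula. The documents do not support that. They name no formula, and several uncorrected approximations give about 80%. Consistency is all that can be claimed.

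**Conclusion.** The point holds as a minor correction. With the plan's own inputs, the named test has 76.8% power, not 80%, and its actual size is about 3.7%. The result rests on a yes/no outcome per patient, exactly 240 evaluable per arm, rates of 85% and 93%, and the usual two-sided definition of Fisher's p-value.

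It would be wrong to read this as a fault in the trial's size. The 534 patients come from days alive and out of hospital (section 10.5). Adherence is exploratory, although it is also Aim 2, and no enrolment, primary or secondary decision depends on this power figure.

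**What to change.** Change one sentence in section 10.4.3.1, before any comparative adherence data are seen. Either:

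- keep Fisher's exact test and state about 77% power at 240 per arm for 85% versus 93% (equivalently, 80% power for a difference of about 8.25 points); or
- name the uncorrected Pearson chi-square test and keep the 80% at 240 per arm. Its exact power is 81.0% and its size about 5.0% at 85%. The plan already allows a chi-square test as an alternative to Fisher's for the mortality and re-hospitalization proportions in the same section.

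Whichever is chosen, name the method behind the power figure. A site-stratified Cochran-Mantel-Haenszel test would match the randomization, but the documents give no site-level rates and its power was not computed, so the 80% should not be attached to it without a calculation.

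The cost is an edit to the text. No extra patients are needed.
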